12.4.4. Grade 3 or 4 infusion reactions to nivolumab

Any CTCAE grade 3 or 4 infusion reactions to nivolumab must be reported as SAEs.

Infusion reactions should be reported from first dose of nivolumab until completion of trial treatment.

See next page for reporting requirements.

Event	Definition	Form required	Timeframe
Grade 3 or 4 infusion reaction to nivolumab	As per CTCAE v5 infusion related reaction: Grade 3: Prolonged (e.g. not rapidly responsive to symptomatic medication and/or brief interruption of infusion); recurrence of symptoms following initial improvement; hospitalisation indicated for clinical sequelae Grade 4: Life threatening consequences; urgent intervention indicated	SAE report	Within 24 hours of infusion reaction occurring

Grade 3 or 4 infusion reactions must be reported on the trial-specific SAE report by fax or email:

[contact]

Email: [contact]

12.5. Urgent events

12.5.1. Post-allogeneic transplant events

The following urgent events for Nivolumab must be reported on the appropriate Urgent Event form within **72 hours of becoming aware of the event** if they occur at any time between transplant day 0 and day 100 post-transplant in patients who receive an allogeneic stem cell transplant following nivolumab.

Event	Description	Form required	Timeframe
Grade 3 – 4 graft versus host disease	Grade 3 or 4 graft versus host disease as assessed by the modified Glucksberg criteria (see Appendix 5)	Post-allogeneic transplant urgent event form	Within 72 hours of becoming aware of event
Hyperacute graft versus host disease	Acute GVHD of any grade occurring within 14 days after stem cell infusion, and prior to neutrophil engraftment (Saliba et al 2007)	Post-allogeneic transplant urgent event form	Within 72 hours of becoming aware of event

Non-infectious febrile episodes requiring steroid therapy	Steroid responsive febrile syndrome is defined as 3 of the following major criteria or 2 major and ≥1 minor criteria: Major criteria	Post-allogeneic transplant urgent event form	Within 72 hours of becoming aware of event
(including steroid- responsive febrile syndrome)	 Non-infectious fever Rash covering >25% of body surface area Non-cardiac pulmonary oedema Minor criteria Bilirubin >17.1 µmol/L Weight gain >2.5% above baseline AST > 2 x ULN Creatinine >2 x baseline Typically occurring within 96 hours of neutrophil engraftment and responsive to corticosteroids (Spitzer 2001) Any non-infectious febrile episodes 		
	treated with steroids, occurring within 42 days post-transplant should be reported, even if the above criteria for a diagnosis of steroid-responsive febrile syndrome are not met.		
Sinusoidal obstruction syndrome (veno- occlusive disease)	2 of the following criteria occurring within 20 days after stem cell infusion: • Bilirubin >17.1 µmol/L • Hepatomegaly and/or tenderness or pain over the liver • Weight gain >20% above baseline	Post-allogeneic transplant urgent event form	Within 72 hours of becoming aware of event

12.5.2. Disease progression

The following event must be reported within **72 hours of becoming aware of the event** on the relevant Urgent Event Form if it occurs at any time during the trial:

Event	Description	Form required	Timeframe
Disease progression	Progression of Hodgkin lymphoma, confirmed by standard local investigations	Disease progression form	Within 72 hours of becoming aware of confirmed progression

12.5.3. Death

The following event must be reported within **24 hours of becoming aware of the event** on the relevant Urgent Event Form if it occurs at any time during the trial:

Event	Description	Form required	Timeframe
-------	-------------	---------------	-----------

Where the cause of death meets the criteria for an SAE (see section 12.2.2. above), an SAE report must also be submitted.

All Urgent Events must be reported on the the relevant
Urgent Event Form by fax or email:
[contact]
Email: [contact]

12.6. Expedited Safety Reports (ESR)

BMS may report other important findings as an Expedited Safety Report (ESR), including: increased frequency of a clinically significant expected SAE, an SAE considered associated with study procedures that could modify the conduct of the study, lack of efficacy that poses significant hazard to study subjects, clinically significant safety findings from a nonclinical (e.g. animal) study, important safety recommendations from a study data monitoring committee, or Sponsor decision to ed or temporarily halt a clinical study for safety reasons.

UCL CTC will forward ESRs received from BMS to all Pls. These must be processed by sites in the same way as SUSARS according to local requirements, and filed with the IB.

12.7. Safety Monitoring

UCL CTC will provide safety information to the Trial Management Group (TMG) and the Independent Data Monitoring Committee (IDMC) on a periodic basis for review.

Trial safety data will be monitored to identify:

- new adverse reactions to the trial treatment regimen or individual trial treatments
- unacceptably high incidence of expected adverse events
- trial related events that are not considered related to the trial treatment regimen

If UCL CTC identifies or suspects any issues concerning patient safety at any point during the trial, the CI or TMG will be consulted for their opinion, and if necessary the issue will be referred to the IDMC.

12.8. Pregnancy

Reporting Period

If a female patient becomes pregnant between the start of trial treatment and 6 months after last trial treatment administration or the female partner of a male trial patient becomes pregnant between the start of trial treatment and 8 months after last trial treatment administration, the site must submit a trial specific Pregnancy Report to UCL CTC by fax or email **within 24 hours** of learning of its occurrence.

The site must request consent from the pregnant trial patient or female partner of a male patient to report further information regarding a pregnancy.

- For female patients, consent for pregnancy monitoring will be sought at study entry, using the trial Patient Information Sheet and Informed Consent Form
- For female partners of male patients: the trial specific Pregnancy Monitoring Information Sheet and Informed Consent Form for partners of study patients will be used in the event of a pregnancy.

If consent is not given, the initial notification that a pregnancy has occurred will be retained by UCL CTC, and an anonymised copy will be forwarded to BMS, however no further action will be taken on the information detailed in the report.

All pregnancies must be reported by faxing or emailing a completed Pregnancy Report to UCL CTC within 24 hours of becoming aware of the pregnancy

[contact] Email: [contact]

Pregnancy Follow-Up Reports

For pregnant patients or partners who consent, their pregnancies must be followed -up until an outcome is determined. Follow-up Pregnancy Reports must be submitted to UCL CTC by fax or email within **24 hours** of learning of the outcome. Reports must include an evaluation of the possible relationship of each trial treatment to the pregnancy outcome.

SAEs during pregnancy

Any SAE occurring in a pregnant patient must be reported using the trial specific SAE Report, according to SAE reporting procedures. Refer to section 12.2.212.2.212.2.2 (Reporting of Serious Adverse Events (SAEs)) for details.

Pregnancy Report processing at UCL CTC

UCL CTC will submit a report to the MHRA and the REC if the pregnancy outcome meets the definition of a SUSAR. Refer to section 12.3 (SUSARs) for details.

UCL CTC will submit all pregnancy reports concerning exposure to Nivolumab to Bristol-Myers Squibb according to the timelines outlined in the agreement between UCL and Bristol-Myers Squibb.

12.9. Development Safety Update Reports (DSURs)

Safety data obtained from the trial will be included in DSURs that UCL CTC will submit to the MHRA and the REC.

UCL CTC will provide Bristol-Myers Squibb with DSURs that include information regarding Nivolumab.

13. INCIDENT REPORTING AND SERIOUS BREACHES

13.1. Incident Reporting

Organisations must notify UCL CTC of all deviations from the protocol or GCP immediately. An incident report may be requested and will be provided, but an equivalent document (e.g. Trust Incident form) is acceptable where already completed.

If site staff are unsure whether a certain occurrence constitutes a deviation from the protocol or GCP, the UCL CTC trial team can be contacted immediately to discuss.

UCL CTC will use an organisation's history of non-compliance to make decisions on future collaborations.

UCL CTC will assess all incidents to see if they meet the definition of a serious breach.

13.2. Serious Breaches

A "serious breach" is defined as a breach of the protocol or of the conditions or principles of Good Clinical Practice (or equivalent standards for conduct of non-CTIMPs) which is likely to affect to a significant degree the safety or physical or mental integrity of the trial subjects, or the scientific value of the research.

Systematic or persistent non-compliance by a site with GCP and/or the protocol, including failure to report SAEs occurring on trial within the specified timeframe, may be deemed a serious breach.

In cases where a serious breach has been identified, UCL CTC will inform the MHRA and REC within 7 calendar days of becoming aware of the breach.

Sites must have written procedures for notifying the sponsor of serious breaches (MHRA Guidance on the Notification of Serious Breaches).

14. TRIAL MONITORING AND OVERSIGHT

Participating sites and PIs must agree to allow trial-related on-site monitoring, Sponsor audits and regulatory inspections by providing direct access to source data/documents as required. Patients are informed of this in the patient information sheet and are asked to consent to their medical notes being reviewed by appropriate individuals on the consent form.

UCL CTC will determine the appropriate level and nature of monitoring required for the trial. Risk will be assessed on an ongoing basis and adjustments made accordingly.

14.1. Central Monitoring

Sites will be requested to submit screening logs and staff delegation logs to UCL CTC at the frequency detailed in the trial monitoring plan, or on request, and these will be checked for consistency and completeness. Also refer to sections 4.2.2 (Required documentation) and 6.1 (Screening Log).

Ensuring patient eligibility is the responsibility of the PI or other delegated Investigator(s). Checks of the criteria listed on the registration form will be undertaken by an appropriately trained UCL CTC staff member prior to registration. Also refer to section 7.1 (Registration).

Details relating to the informed consent process will be collected on the registration form and are subject to review by UCL CTC as part of patient eligibility.

Copies of completed drug accountability logs must be returned to UCL CTC for all trial patients. Sites will be required to submit logs in accordance with the trial monitoring plan.

Data received at UCL CTC will be subject to review in accordance with section 11.4 (Data Queries).

Sites will be requested to conduct quality control checks of documentation held within the Investigator Site File and Pharmacy Site File at the frequency detailed in the trial monitoring plan. Checklists detailing the current version/date of version controlled documents will be provided for this purpose.

Where central monitoring of data and/or documentation submitted by sites indicates that a patient may have been placed at risk (e.g. an overdose has been administered, or data indicate that dose modification rules were not followed following an adverse reaction), the matter will be raised urgently with site staff and escalated as appropriate (refer to section 13 (Incident Reporting and Serious Breaches) and 14.2 ('For Cause' On-Site Monitoring) for further details).

14.2. 'For Cause' On-Site Monitoring

On-site monitoring visits may be scheduled where there is evidence or suspicion of non-compliance at a site with important aspect(s) of the trial protocol/GCP requirements. Sites will be sent a letter in advance outlining the reason(s) for the visit and confirming when it will take place. The letter will include a list of the documents that are to be reviewed, interviews that will be conducted, planned inspections of the facilities and who will be performing the visit.

Following a monitoring visit, the Trial Monitor/Trial Coordinator will provide a follow up email to the site, which will summarise the documents reviewed and a statement of findings, incidents, deficiencies, conclusions, actions taken and/or actions required. The PI at each site will be responsible for ensuring that monitoring findings are addressed in a timely manner, and by the deadline specified.

UCL CTC will assess whether it is appropriate for the site to continue participation in the trial and whether the incident(s) constitute a serious breach. Refer to section 13 (Incident Reporting and Serious Breaches) for details.

14.3. Oversight Committees

14.3.1. Trial Management Group (TMG)

The TMG will include the Chief Investigator, clinicians and experts from relevant specialities and ANIMATE trial staff from UCL CTC (see page 1). The TMG will be responsible for overseeing the trial. The group will meet regularly (approximately quarterly) and will send updates to PIs (via newsletters or at Investigator meetings) and to the NCRI Lymphoma Clinical Studies Group.

The TMG will review substantial amendments to the protocol prior to submission to the REC and MHRA. All PIs will be kept informed of substantial amendments through their nominated responsible individual and are responsible for their prompt implementation.

TMG members will be required to sign a TMG Charter, which describes the committee's responsibilities in relation to the trial and requires any potential conflicts of interest to be declared.

14.3.2. Trial Steering Committee (TSC)

The role of the TSC is to provide overall supervision of the trial. The TSC will review the recommendations of the Independent Data Monitoring Committee and, on consideration of this information, recommend any appropriate amendments/actions for the trial as necessary. The TSC acts on behalf of the funder and the Sponsor.

TSC members will be required to sign a TSC Charter, which describes the committee's responsibilities and requires any potential conflicts of interest to be declared.

14.3.3. Independent Data Monitoring Committee (IDMC)

The role of the IDMC is to provide independent advice on data and safety aspects of the trial. Meetings of the Committee will be held at least once per year to review interim analyses, or as necessary to address any issues. The IDMC is advisory to the TSC and can recommend premature closure of the trial to the TSC.

IDMC members will be required to sign a IDMC Charter, which describes the committee's responsibilities and requires any potential conflicts of interest to be declared.

14.3.4. Role of UCL CTC

UCL CTC will be responsible for the day to day coordination and management of the trial and will act as custodian of the data generated in the trial (on behalf of UCL). UCL CTC is responsible for all duties relating to pharmacovigilance which are conducted in accordance with section 12 (Pharmacovigilance).

15. WITHDRAWAL OF PATIENTS

In consenting to the trial, patients are consenting to trial treatment, assessments, collection of biological samples, follow-up and data collection.

15.1. Discontinuation of Trial Treatment

A patient may be withdrawn from trial treatment whenever such treatment is no longer in the patient's best interests, but the reasons for doing so must be recorded in the patient's notes and on the relevant Case Report Form(s). Reasons for discontinuing treatment may include:

- Disease progression whilst on therapy
- Unacceptable toxicity
- Intercurrent illness which prevents further treatment
- Patient decision not to continue with trial treatment
- Any alterations in the patient's condition which justifies the discontinuation of treatment in the site investigator's opinion
- Non-compliance with the trial treatment and/or procedures
- If a female patient becomes pregnant or male/female patient fails to use adequate birth control (for patients of childbearing potential)

In these cases patients will remain within the trial for the purposes of follow-up and data analysis unless they explicitly withdraw consent.

If a patient expresses their wish to withdraw from trial treatment, sites should explain the importance of remaining on trial follow-up, or failing this of allowing routine follow-up data to be used for trial purposes and for allowing existing collected data to be used. If the patient gives a reason for their withdrawal, this should be recorded.

15.2. Future Data Collection

If a patient explicitly states they do not wish to contribute further data to the trial their decision must be respected, with the exception of essential safety data, and recorded on the relevant CRF. In this event data due up to the date of withdrawal must be submitted but no further data, other than essential safety data, sent to UCL CTC.

15.3. Losses to Follow-Up

See section 15.4 (Transfer of Care) for details of actions needed when a patient relocates or their care is transferred.

If a patient is lost to follow-up at a site every effort should be made to contact the patient's GP to obtain information on the patient's status.

Patients lost to follow up may be tracked by UCL CTC via registries such as the National Cancer Registration and Analysis Service, or the Health & Social Care Information Centre NHS Digital (England), NHS Wales Informatics Service (Wales) or the Information Services Division (Scotland).

15.4. Transfer of Care

For patients moving from the area, every effort should be made for the patient to be followed up at another participating trial site, and for this new site to take over responsibility for the patient's trial visits and data collection going forward.

The process for transferring care to another participating site is as follows:

- Liase with the proposed new site and obtain written confirmation that they are willing to take over follow up duties for the patient.
- Complete a Centre Transfer Form (provided as part of the CRF) and send to UCL CTC.
- CRFs relating to visits up to the point of transfer must be completed and submitted to UCL CTC.
- Provide the new site with copy of the patient's complete CRF up until the point of transfer.

The original site remains responsible for submitting all data due up to the date of transfer, and for resolving any data queries relating to those data. The site to whom the patient is transferred will be responsible for completing CRFs pertaining to visits after the date of transfer only.

Details of participating trial sites can be obtained from the UCL CTC study team upon request.

If the patient cannot be transferred to another participating site, the site that registered them into the trial remains responsible for obtaining and submitting follow up and safety data on the patient.

15.5. Loss of Capacity

If a patient loses capacity during trial treatment, they will be withdrawn from trial treatment, but will remain on trial for follow up and collection of safety data.

If a patient loses capacity after completing trial treatment, they will remain on trial for survival follow up only.

16. TRIAL CLOSURE

16.1. End of Trial

For regulatory purposes the end of the trial will be when the last patient completes three years of follow up, at which point the 'declaration of end of trial' form will be submitted to the MHRA and Ethics Committee, as required.

Following this, UCL CTC will advise sites on the procedure for closing the trial at the site, and notify HMDS and the Weatherall Institute of Molecular Medicine, Oxford.

Once the end of trial has been declared, no more prospective patient data will be collected but sites must co-operate with any data queries regarding existing data to allow for analysis and publication of results.

16.2. Archiving of Trial Documentation

At the end of the trial, UCL CTC will archive securely all centrally held trial related documentation for a minimum of 25 years. Arrangements for confidential destruction will then be made. It is the responsibility of PIs to ensure data and all essential documents relating to the trial held at site are retained securely for a minimum of 25 years after the end of the trial, and in accordance with national legislation.

Essential documents are those which enable both the conduct of the trial and the quality of the data produced to be evaluated and show whether the site complied with the principles of GCP and all applicable regulatory requirements.

UCL CTC will notify sites when trial documentation held at sites may be archived. All archived documents must continue to be available for inspection by appropriate authorities upon request.

16.3. Early Discontinuation of Trial

The trial may be stopped before completion as an Urgent Safety Measure on the recommendation of the TSC or IDMC. Sites will be informed by UCL CTC in writing of the reasons for early closure and the actions to be taken with regards the treatment and follow up of patients.

16.4. Withdrawal from Trial Participation by a Site

Should a site choose to close to recruitment the PI must inform UCL CTC in writing. Follow up as per protocol must continue for any patients recruited into the trial at that site and other responsibilities continue as per the CTSA.

17. QUALITY ASSURANCE

PET QA and central review for this study is being undertaken by the UK PET Core Lab at St. Thomas' Hospital, London.

Please refer to the trial Imaging Manual for more details.

18. STATISTICS

18.1. Sample Size Calculation

Assuming that the overall response rate (ORR) will be around 60% (a conservative estimate based on ORRs of 65-87%; Moskowitz et al. Blood 2014b, Armand et al., 2015, Armand et al. 2016), but to rule out a rate <40% (i.e. BV given pre ASCT; Zinzani et al., 2015), using an A'hern design with 80% power and a one-sided alpha of 0.1 we require 30 patients. We hope to see at least 16 responses (CR or PR).

We assume that 25-40% will be PET positive following first line salvage so in order to treat 30 patients we will need to register 75-120. We will also replace any patient withdrawn before starting nivolumab or who is found to be ineligible after starting treatment. These patients will be excluded from all analyses of the nivolumab treated cohort (including the analysis of the primary endpoint), but will be included in analyses of the total cohort (i.e. all patients registered) if appropriate i.e. if the patients were eligible at this point.

Sample size was calculated using "Sample size tables for clinical studies" software.

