6.2.2. Exclusion criteria – study registration

- 1. Nodular lymphocyte predominant Hodgkin lymphoma
- 2. Women who are pregnant or breastfeeding
- 3. History of colitis, inflammatory bowel disease or pneumonitis
- 4. Patients with autoimmune disorders, except patients with vitiligo, diabetes mellitus type 1, hypo- and hyperthyroidism not requiring immunosuppressive therapy
- 5. Known active hepatitis B or C infection
- 6. Known HIV infection
- 7. History of allergy (including severe/life threatening skin reaction) to monoclonal antibodies, anaphylaxis or uncontrolled allergy
- 8. Major surgery within 4 weeks prior to registration
- 9. Myocardial infarction, unstable angina, coronary artery bypass graft, cerebrovascular accident or transient ischaemic attack within the past 6 months
- 10. Non-haematological malignancy within the past 3 years with the exception of (a) adequately treated basal cell carcinoma, squamous cell skin cancer, or thyroid cancer; (b) carcinoma in situ of the cervix or breast; (c) prostate cancer of Gleason grade 6 or less with stable prostate-specific antigen levels; or (d) cancer considered cured by

surgical resection or unlikely to impact survival during the duration of the study, such as localised transitional cell carcinoma of the bladder or benign tumours of the adrenal gland or pancreas

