18.2. Statistical analysis

18.2.1. Analysis of main endpoint

The primary endpoint is the ORR i.e. the proportion of nivolumab treated patients achieving a response (PMR and CMR compared to end of first or second line salvage treatment scan; PET0) after either 4 (PET4) or 8 cycles (PET8). This will be presented as a proportion with 80% confidence intervals.

Any patient without a response scan will be counted as a non-response for the primary analysis (i.e. the denominator will be all eligible nivolumab treated patients). However, a secondary analysis may also be conducted excluding any patient who drops out before the first response scan for reasons other than disease progression or death from disease.

Analysis of the primary endpoint will take place after all patients have finished nivolumab treatment and response data is available.

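### Patients given nivolumab but later found ineligible are replaced and dropped from every treated-cohort analysis: adverse event tables lose dosed patients, and nothing keeps the ORR exclusion independent of outcome

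*Protocol*

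**What the plan says.** Section 18.1 sets the rule for patients who turn out not to qualify: "We will also replace any patient withdrawn before starting nivolumab or who is found to be ineligible after starting treatment". It continues: "These patients will be excluded from all analyses of the nivolumab treated cohort (including the analysis of the primary endpoint"). Such patients stay in analyses of the total registered cohort only where appropriate, meaning where they were eligible at registration.

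Section 18.2.1 applies the same restriction to the primary endpoint: "the denominator will be all eligible nivolumab treated patients". Eligible treated patients without a response scan count as non-responders.

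Section 18.2.2 describes the adverse event analysis (worst grade per patient, focus on grade 3/4, autoimmune events of any grade). It names no separate safety population and makes no exception to the rule in 18.1. Section 3.2 lists the safety and toxicity of nivolumab, autoimmune toxicity in particular, as a secondary endpoint.

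The design is stated as "using an A'hern design with 80% power and a one-sided alpha of 0.1 we require 30 patients", for a target ORR of 60% against a rate of 40% to be ruled out, with at least 16 responses hoped for.

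**The concern.** Two separate matters follow from one sentence.

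**Safety.** A patient who has received the drug contributes to what is known of its toxicity, whether or not an entry criterion was breached. The words in 18.1 cover all analyses of the treated cohort, and their parenthesis shows that the primary endpoint is only one of them. The total-cohort provision does not cure this. It does not return anyone to the nivolumab toxicity tables. A patient found to have breached a registration criterion, for example "History of colitis, inflammatory bowel disease or pneumonitis" (section 6.2.2), was not eligible at registration and so leaves the total cohort as well.

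**ORR.** Section 18.1 sets no time limit on finding a patient ineligible. It does not say that the finding must rest on data from before the first dose, or that whoever decides must be unaware of the scan results and adverse events. In an open-label single-arm trial, a patient who does badly may have the file looked at more closely. The stated type I error holds only if membership of the 30 does not depend on their outcomes.

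**Working it through.** **Inputs.** From section 18.1: n = 30, cut-off 16, null rate 0.40, target rate 0.60, one-sided alpha 0.10, power 80%. From section 18.2.1: 80% confidence intervals. The protocol gives no number k of treated patients later found ineligible, so k = 1 to 3 is assumed.

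**1. The plan's own figure.** With X ~ Bin(30, p):
- P(X ≥ 16 | p = 0.4) = 0.0971
- P(X ≥ 16 | p = 0.6) = 0.8246

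A search over n finds 30 with cut-off 16 to be the smallest exact design meeting both limits. The sample size is right. The margin below 0.10 is 0.003.

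**2. Exclusion unrelated to response.** The 30 analysed patients each still respond with probability 0.4 under the null, so alpha stays at 0.0971.

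**3. Worst case.** Suppose k non-responders among the first 30 are declared ineligible and each is replaced by a new patient who responds with probability 0.4. With B ~ Bin(k, 0.4):

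alpha(k) = P(X ≥ 16) + Σ P(X = 16 − j) · P(B ≥ j), for j = 1 to k.

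At p = 0.4, P(X = 15) = 0.1754 − 0.0971 = 0.0783. Successive binomial terms give P(X = 14) = 0.0783 × (15/16) × 1.5 = 0.1101 and P(X = 13) = 0.1101 × (14/17) × 1.5 = 0.1360.

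- k = 1: 0.0971 + 0.0783 × 0.4 = 0.128
- k = 2: 0.0971 + 0.0783 × 0.64 + 0.1101 × 0.16 = 0.165
- k = 3: 0.0971 + 0.0783 × 0.784 + 0.1101 × 0.352 + 0.1360 × 0.064 = 0.206

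One such replacement takes alpha past 0.10.

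**4. The estimate.** Suppose 16 of 30 eligible patients respond and the k excluded patients did not. The intervals are exact (Clopper–Pearson), which is an assumption because the protocol names no method.

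| Set | ORR | Lower 80% limit | Cut-off for exact alpha ≤ 0.10 |
|---|---|---|---|
| Eligible only, 16/30 | 53.3% | 40.1% | 16 |
| All treated, 16/31 | 51.6% | 38.7% | 17 |
| All treated, 16/32 | 50.0% | 37.4% | 17 |
| All treated, 16/33 | 48.5% | 36.2% | 18 |

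The eligible-only lower limit just clears 40%. Adding back one non-responder puts it below.

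**5. Safety illustration.** Assume that 6 of 30 eligible patients have a grade 3/4 event and that all k excluded patients also had one. The table would show 6/30 = 20.0%. Among all dosed patients the rate would be 7/31 = 22.6%, 8/32 = 25.0% or 9/33 = 27.3%. If the excluded patients had no events, the difference would run the other way. The direction depends on who is excluded.

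**The case against.** The best defence is that few patients should be affected and that safety data are not lost. Section 14.1 has the trials centre check criteria before registration. Section 7.2 has treatment eligibility confirmed centrally with central PET review, and section 9.2 bars nivolumab until that is done. Adverse events are recorded from the first dose without regard to eligibility (12.2.1). SAE reports on patients who received nivolumab go to the manufacturer (12.2.2), and the IDMC reviews all trial data yearly (18.2.2). The exclusion sentence sits under sample size and names only the primary endpoint. All of this stands as a limit on the size of the problem. It does not change what 18.1 says about analysis. A statistical analysis plan could define an all-dosed safety set only by contradicting that sentence.

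A reader might infer more than the documents support, in three ways.

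- **That toxicity goes unreported.** It does not. Only the analysed, published summaries are affected.
- **That the excluded patients are those most prone to autoimmune toxicity.** Some criteria do concern colitis, pneumonitis or autoimmune disease. Many others concern histology, Deauville score, blood counts, renal function, recent surgery or other malignancy. The protocol gives no distribution of reasons for late ineligibility. One plausible route, central pathology review of tumour blocks sent after registration (9.1 and 10), has nothing to do with toxicity.
- **That the optional secondary ORR compounds the fault** by "excluding any patient who drops out before the first response scan for reasons other than disease progression or death from disease". The primary analysis already counts eligible treated patients without a scan as failures. The secondary one only may be done and has no success criterion attached.

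The alpha figures above 0.097 also assume that every excluded patient was a non-responder. No figure in the protocol supports any particular k.

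**Conclusion.** The point holds in two parts. First, sections 18.1 and 18.2.2 read together remove dosed patients from the adverse event and AESI analyses of a trial in which nivolumab safety is a secondary endpoint. This follows from the wording and needs no assumption. Its numerical effect is unknown: each such patient would be roughly 3% of a cohort of 30 (1/30 = 3.3%).

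Second, the ORR rule leaves outcome-related exclusion possible. It does not show that any would occur. Exact alpha lies between 0.097, if ineligibility is unrelated to response, and 0.128, 0.165 or 0.206 in the worst case for one, two or three replaced non-responders. Because the design uses nearly all of its 0.10, a single case is enough to matter.

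This should be fixed. The central pre-dose checks and intact safety capture keep it from being a fatal flaw.

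**What to change.** 1. In 18.1 and 18.2.2, state that safety is analysed in every patient who received at least one dose of nivolumab, whatever their eligibility.
2. In 18.1 and 18.2.1, report ORR in all treated patients alongside the eligible-treated result. Allow exclusion and replacement of a treated patient only where ineligibility is shown by data from before the first dose and is decided by people unaware of response and adverse event outcome. List each excluded treated patient with reason, response and adverse events.

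If exclusion is kept, replacement should be kept with it. With 29 patients, a cut-off of 16 gives power 0.766 and a cut-off of 15 gives alpha 0.136, so neither meets the design.

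The cost is wording and a short decision procedure, with no patients or assessments beyond those already planned. The reported ORR may be slightly less favourable.
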